Honest Open and Proud (HOP) programme, which is a peer-led approach, provides an opportunity for patients to discuss mental health stigma and explore their disclosure decisions with peers has shown promise. This has recently been modified and changed to Let's Talk through review of the workbook, manual and through Public and Patient Involvement. Three pilot randomised controlled trials (RCTs)³⁻⁵ have looked at the efficacy of Let's Talk but none of these have been conducted in the UK or with those experiencing psychosis.

2. Study Aims and Objectives

The principal objective is to evaluate the feasibility and acceptability of conducting a RCT of the 'Let's Talk' per-delivered intervention with people who experience psychosis.

The specific objectives of the trial are to assess:

 The proportion of eligible people clinicians are willing to refer, the proportion of eligible people willing to participate, the proportion of participants who engage with the intervention

- 2. The proportion of participants who select in-person vs. remote delivery of the Let's Talk peer-delivered intervention.
- 3. The drop-out rate.
- 4. The characteristics of trial participants to refine selection criteria.
- 5. The appropriateness and integrity of Let's Talk workbook and manual.
- 6. The feasibility and acceptability of the intervention to participants.
- 7. The randomisation procedures.
- 8. The relevance (to participants) and validity of the measures to assess effectiveness, service use, health status, safety and acceptability in a subsequent definitive trial.

3. General Study Design

A feasibility trial of a pragmatic, parallel group patient randomised superiority trial comparing Let's Talk plus treatment as usual (TAU) or TAU alone.

4. Interventions to be evaluated

Let's Talk plus treatment as usual: Let's Talk is an adaptation of the HOP program. HOP comprises of a workbook and manual and is delivered in a group format by one or more facilitators trained in the manual and at least one facilitator that has lived with experience of a mental heal problem³⁻⁵. Let's Talk has been adapted to ensure localisation to the UK context and delivery in a one-to-one setting by a peer support worker with up to 10 weeks of the programme.

Treatment as usual: this includes early intervention in psychosis and secondary care adult mental health services.

5. Randomisation, Allocation and Blinding

All participants who agree to enter the study will be logged with the central trial office and given a unique Study Number. Randomisation will utilise the existing proven remote automated computer randomisation application in the central trial office in the Centre for Healthcare Randomised Trials (CHaRT, a fully registered UK CRN clinical trials unit) in the Health Services Research Unit (HSRU), University of Aberdeen. Randomisation will be computer-allocated using randomised-permuted blocks of random size. The unit of randomisation will be the participant and on a 1:1 ratio stratified by centre and delivery mode (in person or remote). No blinding of the treatment allocation will be done.

6. Outcome Measures

6.1. Feasibility outcomes

As it is a feasibility study, a single primary outcome is not meaningful. The key outcomes are (these will be tabulated and not analysed):

- 1. Referral rates;
- 2. Recruitment;
- 3. Attendance at the Let's Talk sessions (number of sessions);
- 4. Fidelity to the Let's Talk strategies and peer principles Follow-up/questionnaire; response rates.

6.2. Outcome measures

Outcomes measures will be collected to determine their suitability for use in a definitive trial and identify a suitable primary outcome for a definitive trial, rather than to draw conclusions about efficacy of treatments. In addition to demographics, we will collect the following outcomes:

- 1. The Semi-structured Interview Measure for Stigma in Psychosis (SIMS)⁶;
- 2. Disclosure Stress Scale (DDS)⁵;
- 3. Stigma Stress Scale⁷;
- 4. The Process of Recovery Questionnaire (QPR)⁸;
- 5. The Calgary Depression Rating Scale for Schizophrenia (CDS)⁹;
- 6. Social Interaction Anxiety Scale (SIAS)¹⁰;
- 7. Manchester Short Assessment of Quality of Life Scale (MANSA)¹¹;
- 8. Rogers Empowerment Scale (RES)¹²;
- 9. Economic patient questionnaire¹³;
- 10. EuroQol Group's 5-dimension health status questionnaire 5 level (EQ5D-5L)¹⁴.

6.3. Mediators

We will collect data on the below potential mediators of change to determine feasibility of collecting these measures in a definitive trial to answer important hypotheses about mediators:

- 1. Internalised Shame Scale (ISS)¹⁵;
- 2. Self-Esteem Rating Scale (SERS)¹⁶.

7. Timing of Outcome Measurements

Outcome Measure	Baseline	End of treatment (2.5	6 months ¹
		months ¹)	
SIMS	~	√	√
DDS	~	\checkmark	\checkmark
Stigma Stress Scale	~	\checkmark	\checkmark
QPR	~	\checkmark	\checkmark
CDS	✓	\checkmark	\checkmark
SIAS	✓	\checkmark	\checkmark
MANSA	✓	\checkmark	\checkmark
RES	~	\checkmark	\checkmark
Economic patient	✓	\checkmark	\checkmark
questionnaire			
EQ5D-5L	✓	✓	\checkmark
ISS	✓	✓	\checkmark
SERS	\checkmark	\checkmark	\checkmark

¹ post-randomisation

8. Progression criteria

The progression criteria to a definitive trial are:

- Recruitment rate within ≥80% (green); 79-60% (amber); <60% (red) of planned target.
- Retention of participants within the study with ≥ 80% (green); 79-60% (amber);
 <60% (red) of data for the Semi-structured Interview Measure of Stigma (SIMS⁶)

or Stigma Stress Scale⁷, which are the proposed primary outcomes for a definitive trial.

 ≥ 80% (green); 79-60% (amber); <60% (red) of those allocated to Let's Talk receiving at least two sessions.

9. Adverse Events

A serious adverse event (SAE) is:

- All death;
- Suicide attempts;
- Serious violent incidents;
- Any other life-threatening incident;
- Admissions to a psychiatric hospital;
- Formal complaints about the study.

Please see the Study Protocol for more details on AEs. The number SAEs and the proportion of participants with an event will be presented. These will be tabulated and not analysed and will be summarised by Intention-to-Treat (ITT) and as treated.

10. Sample Size and Power Calculation

Outcome data on 60 participants is needed to estimate the standard deviation (SD) required for a sample size calculation for a definitive trial. We have used the advice from Whitehead et al¹⁷ to plan ahead for a trial with 90% power and potential small-to-moderate effect size (standardised effect size ranging from 0.2 to 0.4). To allow 20% attrition, we will recruit 75 participants. A pilot study of this size will allow to test procedures and gather information on other trial design and process elements that are listed in the objectives section.

11. Statistical Methods

11.1. General Methods

All the main analyses will be based on the ITT principle. Final analysis will take place after full recruitment and follow-up. The results of the trial will be presented following the Consolidated Standards of Reporting Trials (CONSORT) 2010 Statement: extension to randomised pilot and feasibility trials¹⁸. As this is a feasibility trial, the main focus will be to summarise baseline and follow-up data using the appropriate descriptive statistics and graphical summaries. However, we will also look at treatment effects which will be presented with 95% confidence intervals (CIs). There will be no adjustment to secondary outcomes for multiple testing. All eligible participants will be included in the analysis and who provided consent. Any post-randomisation exclusions will be removed and reported as such and agreed with the PMG. Model assumptions will be checked and dealt with appropriately. See Appendix (section 16) for how patient reported outcome measures (PROMS) are derived along with Stata code for the analysis of the outcomes.

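### The SAP labels its main analyses intention-to-treat (ITT), but limits them to eligible participants and allows open-ended removals after randomisation, so the analysis set is not ITT and retention has no fixed denominator

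*SAP*

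**What the plan says.** Three statements stand in the same paragraph of SAP Section 11.1 (General Methods):

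- On the analysis principle: "All the main analyses will be based on the ITT principle"
- On who is analysed: "All eligible participants will be included in the analysis and who provided consent"
- On removals once people have been randomised: "Any post-randomisation exclusions will be removed and reported as such and agreed with the PMG"

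On masking, Section 5 says: "No blinding of the treatment allocation will be done".

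Section 8 sets three progression criteria with a green cut-off of 80%. Recruitment is judged against the planned target ("Recruitment rate within ≥80% (green); 79-60% (amber); <60% (red) of planned target"). Session receipt is judged among those allocated to Let's Talk. Retention is judged on the availability of SIMS or Stigma Stress Scale data, with no explicit denominator.

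Section 10 gives the planned size: "Outcome data on 60 participants is needed to estimate the standard deviation (SD) required for a sample size calculation for a definitive trial" and "To allow 20% attrition, we will recruit 75 participants".

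Section 6.2 says the outcome measures are not collected to draw efficacy conclusions. Even so, Section 11.1 promises treatment effects with 95% confidence intervals, and Table 13.4 has columns for mean difference, interval and p-value.

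**The concern.** ITT means that everyone randomised is analysed in the arm they were allocated to. The second and third statements describe something narrower: an eligible-only set from which people can be removed after randomisation by agreement with the PMG. At best that is a modified ITT set, and the SAP neither calls it that nor defines it.

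The removal rule is open-ended. It is not restricted to facts fixed before randomisation, has no time limit, and does not require the decision to be made without knowledge of arm or outcome. Allocation is open, so the SAP contains no safeguard against removals that depend on arm or on how a participant fared. Reporting an exclusion makes it visible but does not restore the randomised comparison. Section 11.7 plans no formal analysis for missing outcome data that could serve as a check.

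Three uses of the data are affected:

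- the treatment effects in Table 13.4;
- the SD that Section 10 wants for sizing the definitive trial;
- the retention criterion in Section 8, if the removals carry through to its denominator.

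In a feasibility trial, people randomised and then judged unsuitable are also a finding in themselves. Section 2 lists the drop-out rate, refinement of the selection criteria and the randomisation procedures among its objectives.

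**Working it through.** **Reproducing the plan's figure.** 60 with outcome data and 20% attrition gives 60/(1 − 0.20) = 75, which matches Section 10. The 75 allows for attrition only and has no separate allowance for post-randomisation exclusions. It also puts planned retention exactly on the boundary: 60/75 = 80.0%. A result close to the cut-off is therefore plausible.

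**Retention.** Let x be the number with data and k the number removed. The SAP gives neither, so the counts below are assumptions, taken near the cut-off to show sensitivity.

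| Case | All 75 randomised | After removal |
|---|---|---|
| 2 removed, neither has data: x/(75 − k) | 59/75 = 78.7% | 59/73 = 80.8% |
| 3 removed, none has data: x/(75 − k) | 58/75 = 77.3% | 58/72 = 80.6% |
| 2 removed, both have data: (x − k)/(75 − k) | 60/75 = 80.0% | 58/73 = 79.5% |

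The first two rows move from amber to green. The third moves from green to below green (58/73 = 0.7945, so 79% as a whole percent). The direction depends entirely on who is removed.

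**Recruitment.** The denominator is the planned target, which is fixed. Taking exclusions off the count can only lower the figure, for example from 75/75 = 100% to 72/75 = 96% with three removed.

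**Session receipt.** Section 8 already fixes the denominator as those allocated to Let's Talk. It would change only if the Section 11.1 rule overrode it, and the SAP does not say that it does.

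**Treatment effect.** Suppose k of n participants in one arm are removed and their mean differs by d SD from the rest of that arm. The arm mean, and so the mean difference, shifts by (k/n) × d SD. Section 5 allocates 1:1, so take n = 30 per arm from the 60 in Section 10. The values of k and d are assumed:

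- k = 1, d = 0.5: 1/30 × 0.5 = 0.02 SD
- k = 2, d = 1: 2/30 × 1 = 0.07 SD
- k = 3, d = 2: 3/30 × 2 = 0.20 SD

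For scale, the unadjusted 95% confidence interval half-width is 1.96 × √(2/30) = 0.51 SD, and Section 10 plans for standardised effects of 0.2 to 0.4. If exclusions rest only on pre-randomisation facts and are made without regard to arm, the systematic shift is zero.

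**The case against.** Several points on the other side are sound.

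- **The grounds may be in the protocol.** The SAP is based on protocol version 5, which is not at hand, and eligibility and withdrawal rules often sit there. So the absence of grounds can be asserted only of the SAP. The conflict between the ITT statement and the removal rule is nevertheless in the SAP's own text.
- **Eligible may simply mean screened as eligible before randomisation.** On that reading the eligibility sentence is harmless. The next sentence still removes people after randomisation.
- **Excluded people do not disappear.** Exclusions must be reported, the SAP commits to the CONSORT extension for pilot and feasibility trials, and it lists a participant-flow figure. This stands, and it limits the harm.
- **Efficacy is not the aim.** The illustrative shift of 0.02 to 0.20 SD is well inside the half-width of 0.51 SD. This also stands. No efficacy decision rests on the set, though the effects are still tabulated with p-values.

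Stronger readings are tempting, and the SAP does not support them:

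- **That removals inflate the feasibility percentages.** They cannot raise recruitment, the session criterion is already tied to allocation, and retention can move either way.
- **That the effects are biased.** The number and the grounds of exclusions are unknown, so the most that can be said is that bias is possible.
- **That the PMG decides with knowledge of outcomes by arm.** The SAP says only that allocation is not blinded and that the PMG agrees exclusions. What the PMG sees is an inference.
- **That withdrawals are treated as exclusions.** The SAP nowhere says so.

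**Conclusion.** Section 11.1 contradicts itself. The set it describes is not ITT, and the SAP states neither the grounds for removal nor any requirement to decide without sight of arm or outcome. This is a stated rule that permits a non-ITT comparison, so it goes beyond missing detail.

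The size is modest and conditional. Two or three removals could change the retention colour in either direction, but only if the result lies near 80% and the removals are applied to that denominator, which the SAP leaves open. The possible shift in a treatment effect is about 0.02 to 0.20 SD, assuming one to three selective removals from one arm of 30 and a gap of 0.5 to 2 SD. The upper end equals the bottom of the effect range planned for, but is smaller than the sampling uncertainty.

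The text should be corrected before analysis, because the correction is simple and the retention result feeds the decision to proceed.

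**What to change.** In Section 11.1, replace the eligibility sentence and the removal sentence with:

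*The analysis set is all randomised participants in their allocated arm; data are left out only where consent to use them is withdrawn or was never valid; participants found ineligible after randomisation stay in and are listed by arm with reasons.*

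In Section 8, state that the retention denominator is all randomised participants. Confirm that the session criterion keeps all those allocated to Let's Talk as its denominator, regardless of Section 11.1.

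If the PMG wants an eligible-only set, label it a sensitivity (modified ITT) summary. Limit its exclusions to facts fixed before randomisation, and have them decided blind to arm and outcome.

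The cost is SAP wording only, with no new data. The downside is that the percentages may look slightly less favourable.

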11.2. Interim Analysis

There are no planned interim analyses for efficacy or futility but an independent Data Monitoring Committee (DMC) will monitor trial progress and specifically any safety issues.

11.3. Feasibility Outcomes

Descriptive statistics will be used to summarise the key indicators of the success of the trial (see section 6.1 for details if these indicators).

11.4. Outcome measures

To inform a definitive trial analysis, the proposed outcomes (see section 6.2, apart from economic patient questionnaire) will be analysed using repeated-measures mixed-effects regression model correcting for baseline score and time as a categorical fixed effect and centre, mode of delivery, and participant as a random effect. The repeated measures will be assessed at 2.5 and 6 months post-randomisation with treatment effects estimates from a time-by-treatment interactions at each time point. Data missing at baseline will be reported as such. For the analysis, missing baseline data will be imputed using the centre-specific mean of that variable. Economic data collected by the economic patient questionnaire will be summarised using appropriate descriptive statistics.

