16.2. Stata code

Table 16.2 provides sample Stata code for the analysis, each outcome (see section 6.2) will be analysed the same therefore the code below will be used for all outcomes.

Outcome	Stata code
SIMS	<pre>mixed sims sims_b i.letstalk##i.TimePoint CentreNo: deleverymode: StudyNo: c sims sq is continuous sims _b is continuous baseline score letstalk binary (coded 0 for TAU and 1 Let's Talk plus TAU TimePoint is a categorical variable corresponds to the follow-up time points (coded 2 = 2.5 months, 6 = 6 months) CentreNo categorical (corresponds to each recruiting centre) deleverymode 0 = in person; 1 = remote StudyNo is a unique participant identifier Treatment effect for 2.5 months lincomest _b[1. letstalk] Treatment effect for 6 months lincomest _b[1. letstalk] + _b[1. letstalk #6.TimePoint]</pre>

Table 16.2 Stata code

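### The outcome model forces one residual variance and one baseline slope on both visits, so its 95% CIs at 2.5 and 6 months are miscalibrated in opposite directions if these differ

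*SAP*

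**What the plan says.** Section 11.4 of the SAP specifies a repeated-measures mixed model, "correcting for baseline score and time as a categorical fixed effect and centre, mode of delivery, and participant as a random effect". On the effects to be reported it says: "The repeated measures will be assessed at 2.5 and 6 months post-randomisation with treatment effects estimates from a time-by-treatment interactions at each time point".

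The sample code in Table 16.2 has the same form: "sims_b i.letstalk##i.TimePoint CentreNo: deleverymode: StudyNo". The baseline score enters once, and only treatment is crossed with time. Section 16.2 adds that "each outcome (see section 6.2) will be analysed the same therefore the code below will be used for all outcomes". Section 11.4 leaves out the economic questionnaire, so nine outcomes are modelled this way.

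Neither place gives a baseline-by-time term or a residual variance that may differ by visit. Table 13.4 has columns for the mean difference, 95% CI and p-value, and also shows the raw mean, SD and n by arm at each visit. Section 11.1 says of the model only: "Model assumptions will be checked and dealt with appropriately".

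**The concern.** A participant random intercept plus one residual variance is compound symmetry, so the outcome has the same model variance at 2.5 and 6 months. A single baseline term makes the baseline score predict both visits with the same slope. The first visit is the end of treatment and the second comes 3.5 months later. The plan gives no reason to expect equal spread, or equal prediction from baseline, at the two.

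The SAP reports a separate effect with its own interval at each visit. If the constraint is wrong, the common standard error is too large at one visit and too small at the other, and the p-values follow. The baseline-adjusted precision at each visit, which is useful when a definitive trial chooses its time point, is averaged away.

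**Working it through.** **The plan's own figure.** Section 10 needs outcome data on 60 participants and allows 20% attrition: 60 / (1 − 0.20) = 75, as stated. The SAP gives no standard error or interval width for the model, so there is nothing further to reproduce.

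**Inputs.** From the SAP: 60 participants with outcome data, 1:1 allocation (30 per arm), two visits, 95% intervals. Assumed, because the SAP gives none: SD 1 at baseline and 2.5 months; 6-month SD s between 1.0 and 1.3; baseline correlations r1 (2.5 months) and r2 (6 months) from 0.6/0.6 to 0.7/0.5.

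**Formulas (complete data).**
- Visit-specific baseline slopes: b1 = r1 and b2 = r2·s. The model fits their average, b = (b1 + b2)/2.
- Residual variance around that common slope: v1 = 1 − 2·b·b1 + b² and v2 = s² − 2·b·b2 + b².
- The model uses the mean, v = (v1 + v2)/2, at both visits, so model SE = √(4v/60) twice.
- True SE at visit t = √(4·v_t/60). Coverage = 2Φ(1.96·√(v/v_t)) − 1.

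The between-visit correlation drops out of these expressions.

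**Worked case, s = 1, correlations 0.7 and 0.5.** b = 0.6; v1 = 1 − 0.84 + 0.36 = 0.52; v2 = 1 − 0.60 + 0.36 = 0.76; v = 0.64. Model SE = √(4 × 0.64/60) = 0.207 at both visits. True SEs are √(4 × 0.52/60) = 0.186 and √(4 × 0.76/60) = 0.225.

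| 6-month SD | r1 / r2 | Model SE, both visits | True SE 2.5 / 6 mo | Coverage 2.5 / 6 mo |
|---|---|---|---|---|
| 1.0 | 0.6 / 0.6 | 0.207 | 0.207 / 0.207 | 95.0% / 95.0% |
| 1.1 | 0.6 / 0.6 | 0.217 | 0.207 / 0.227 | 96.1% / 93.9% |
| 1.0 | 0.7 / 0.5 | 0.207 | 0.186 / 0.225 | 97.0% / 92.8% |
| 1.2 | 0.6 / 0.6 | 0.229 | 0.207 / 0.248 | 97.0% / 92.9% |
| 1.2 | 0.7 / 0.5 | 0.231 | 0.185 / 0.269 | 98.6% / 90.7% |
| 1.3 | 0.7 / 0.5 | 0.243 | 0.185 / 0.291 | 99.0% / 89.9% |

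**Simulation of the fitted model.** The participant-intercept model was fitted by maximum likelihood with 1.96 intervals to 500 data sets per scenario. The between-visit correlation was 0.7, and the centre and delivery-mode effects were left out. Monte Carlo error on coverage is about √(0.95 × 0.05/500) = 1 point.
- Complete data: the two model SEs were identical in every scenario (0.202/0.202 in the equal case). In the SD 1.2, 0.7/0.5 case they were 0.225/0.225 against empirical 0.173/0.278, with coverage 98.6%/89.0%.
- Same case with 20% of 6-month data missing: model SEs 0.219/0.238 against empirical 0.184/0.294, with coverage 97.4%/87.8%. The model ratio is 0.238/0.219 = 1.09; the empirical ratio is 0.294/0.184 = 1.60.

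**After the change.** With a visit-specific slope and variance, the SEs are √(4(1 − r1²)/60) and √(4s²(1 − r2²)/60). For correlations 0.7/0.5 they are 0.184/0.224 with s = 1 and 0.184/0.268 with s = 1.2. With 0.6/0.6 and s = 1 both are 0.207, so nothing is lost when the constraint is true. In 15,000 simulated trials per scenario with t-based intervals, coverage under this form was 95.0%/95.2%.

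**The case against.** The strongest reply is that the error is conditional on facts the SAP does not supply. That stands. A reader might infer that one interval is bound to be too wide and the other too narrow. The document does not support this: it gives no visit-specific SD or correlation, so whether there is an error, how large it is and which visit it favours all remain open. The first row of the table shows no error at all.

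A reader might also infer that the relative precision of the two visits cannot be seen. That goes too far, because Table 13.4 reports raw SDs by visit. Only the baseline-adjusted precision is hidden. Nor will the two SEs be exactly equal in practice: with attrition they separate somewhat, though in the case simulated far less than the true ones do.

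The plan does promise to check assumptions, and it calls the code a sample. But it names no check, trigger or alternative structure, and it applies the one form to all modelled outcomes. The printed code line has lost symbols in text extraction, so the absence of a residual option there is weak evidence alone. The prose of 11.4 describes the same model.

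Finally, section 6.2 disclaims efficacy conclusions, section 11.1 puts description first, and the progression criteria in section 8 rest on recruitment, retention and attendance. The footnote to Table 13.1, garbled in extraction, also appears to treat 2.5 months as the primary time point for response rates, and in the scenarios above that visit's interval is conservative. This limits the weight of the point but does not remove it, since the intervals and p-values will still be reported.

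**Conclusion.** The point holds in conditional form. The specified model ties residual variance and baseline slope across the two visits. It therefore returns the same SE for both effects with complete data, and nearly the same with moderate dropout. If the visits differ, coverage is off by about 1 point for a 6-month SD ratio of 1.1, about 2 points for baseline correlations of 0.7 and 0.5, and about 4 points for both the fall in correlation and an SD ratio of 1.2, high at one visit and low at the other. If they do not differ, the intervals are correct. All these sizes rest on assumed SDs and correlations, 60 completers and a large-sample formula. Severity is low, because no conclusion or progression decision depends on these intervals.

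**What to change.** In section 11.4, state that the baseline score interacts with time and that the two follow-up measurements within a participant have an unstructured residual covariance. In Table 16.2, replace `sims_b` with `c.sims_b##i.TimePoint`. At the `StudyNo` level, replace the random intercept with `noconstant residuals(unstructured, t(TimePoint))`. Keep the two treatment contrasts as they are.

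The cost is one sentence, one line of code and two extra parameters: one more slope, and three covariance parameters instead of two. With only two follow-up visits, convergence should not be a concern.

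The change does not alter the small-sample behaviour of maximum likelihood with normal-based intervals. For a separate-visit ANCOVA with 60 participants and 57 residual degrees of freedom, coverage under that method is P(|t57| < 1.96 × √(57/60)) = 93.9% at either visit. The 95.0%/95.2% above is for t-based intervals with REML-type variances, and the choice of method is a separate matter.

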12. COVID-19

The effect of COVD-19 defined as 11th March 2020 ²⁰ or after will be explored. In the first instance, periods before, during and after COVID-19 will be summarised using appropriate descriptive statistics and graphical summaries. If need be, formal analysis will be carried out to explore the effect of COVID-19.

13. Dummy Tables

Table 13.1 Feasibility outcomes

	Let's Talk + TAU N=	TAU N=	Total N=
Referral rates – n (%)	NA	NA	
Recruitment – n (%)	NA	NA	
Attendance at the Let's Talk sessions		NA	
(number of sessions) ¹ – n (%)			
≥ 80%			
60 -79%			
<60%			
Fidelity to the Let's Talk manual and		NA	
principles of peer support and the most used			
Let's Talk strategies – n (%)			
Fidelity to peer principles			

Most used strategies (all sessions	
and by session)	
Fidelity to the Let's Talk strategies – n (%)	NA
Fidelity to peer principles	
Most used strategies (all sessions	
and by session)	
Follow-up/questionnaire response rates ² – n	
(%)	
SIMS Total	
Stigma stress	
¹ of those receiving at least two sessions. This will also be summarised by delivery mothe primary end point but 6 months will also be reported.	ode. ² 2.5 months is

Table 13.2 Recruitment by centre

Centre	Let's Talk + TAU N=	TAU N=
Greater Manchester Mental health NHS foundation trust		
North East London NHS Foundation Trust		

Table 13.3 Baseline characteristics

	Let's Talk + TAU N=	TAU N=
Age – mean (SD); n		
Gender – n (%)		
Female		
Male		
Nonbinary		
Prefer not to say		
Transgender male		
Transgender Female		
Other		
Highest level of education – n (%)		
Primary		
Secondary		
Further		
Higher		
Employment status – n (%)		
Full-time		
Part-time		
Voluntary		
College student		
University student		
Carer		

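### Centre and delivery mode have two levels each but are fitted as random effects: their variances will be very imprecise and often zero, so fit both strata as fixed effects

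*SAP*

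**What the plan says.** - **Model text.** Section 11.4 specifies a repeated-measures mixed model "correcting for baseline score and time as a categorical fixed effect", with "centre, mode of delivery, and participant as a random effect". It covers every outcome in Section 6.2 except the economic questionnaire: 10 − 1 = 9 outcomes. The stated purpose is to inform the definitive trial's analysis.
- **Model code.** Table 16.2 begins "mixed sims sims_b i.letstalk##i.TimePoint CentreNo: deleverymode: StudyNo". Some separators were probably lost when the PDF was read, which is not a fault of the plan. Centre and mode appear only as random-effect levels, in the order centre, mode, participant, with no fixed term for either. Section 16.2 applies this code to all outcomes.
- **Levels.** Table 13.2 lists "Greater Manchester Mental health NHS foundation trust" and "North East London NHS Foundation Trust" and no other centre. Mode is coded "deleverymode 0 = in person; 1 = remote".
- **Randomisation.** Section 5 allocates 1:1, "stratified by centre and delivery mode (in person or remote").
- **Fallback.** Section 11.1 says only, in general terms, that model assumptions will be checked and dealt with. There is no rule for a variance estimated as zero.

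**The concern.** Randomisation is stratified on both factors, so the analysis should condition on both in a way fixed beforehand. A random effect adjusts only to the extent that its estimated variance is above zero, and two levels say very little about a variance. In-person and remote are also the only two modes, not a sample from a population of modes.

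Text and code differ as well. Section 11.4 lists mode as a separate random effect, whereas successive random-effects equations in Stata's `mixed` are nested. The code's order therefore gives four centre-by-mode cells within two centres and no common mode effect.

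What is at stake is a predictable adjustment that is the same for all nine outcomes, in a model offered as a template for the definitive trial. Section 11.1 promises 95% confidence intervals for treatment effects, and Table 13.4 adds p-values.

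**Working it through.** **The plan's own figure.** Section 10 needs outcome data on 60 participants and allows 20% attrition: 60 / (1 − 0.20) = 75, as stated. It is not in dispute; N = 60 is used below.

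**Assumptions not in the SAP.** True centre and mode differences are each 0 to 0.8 residual SD. Centres are split 50/50, and the remote share is 50% unless stated. Simulations use participant-level means, not the full two-visit model. ML is taken as the main case because no REML option is visible in the code; REML is shown beside it.

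**Step 1: precision of a two-level variance.** Degrees of freedom = 2 − 1 = 1. The 95% limits multiply the estimate by 1/χ²(0.975; 1) = 0.20 and 1/χ²(0.025; 1) ≈ 1018. On the SD scale the factors are 0.45 and 32. If mode is nested, its variance has 4 cells − 2 centres = 2 degrees of freedom, which is little better.

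**Step 2: chance that one such variance is estimated as zero.** With balanced levels and a large-sample approximation, this happens when the 1-df between-level chi-square falls below 2 (ML) or 1 (REML). With a true difference d, the noncentrality is N·d²/4; for d = 0.3 it is 60 × 0.09 / 4 = 1.35.

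**Step 3: both variances together.** Simulation with 400 trials per setting; Monte Carlo SE at most √(0.5 × 0.5 / 400) = 2.5 points. Entries are % of trials.

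| True difference (SD) | 0 | 0.2 | 0.3 | 0.5 | 0.8 |
|---|---|---|---|---|---|
| One two-level variance zero, ML (step 2) | 84 | 72 | 60 | 30 | 5 |
| One two-level variance zero, REML (step 2) | 68 | 55 | 42 | 17 | 2 |
| Nested ML, at least one zero | 97 | 95 | 89 | 72 | 59 |
| Nested ML, both zero | 64 | 50 | 37 | 8 | 0 |
| Nested REML, both zero | 50 | 37 | 22 | 4 | 0 |
| Crossed ML, both zero | 69 | 54 | 37 | 9 | 0 |
| Crossed REML, both zero | 47 | 30 | 16 | 4 | 0 |

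The rows for both variances zero are the ones that count: only then is the adjustment fully lost. With a 20% remote share, nested ML gives 76% at no difference and 44% at 0.3 SD.

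**Step 4: treatment contrast.** Simulation with 600 trials per setting, in residual SD units.

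| True difference (SD) | 0 | 0.3 | 0.5 | 0.8 |
|---|---|---|---|---|
| Mean SE, strata omitted | 0.2599 | 0.2654 | 0.2743 | 0.2991 |
| Mean SE, nested random effects, ML | 0.2516 | 0.2524 | 0.2528 | 0.2540 |
| Mean SE, fixed effects | 0.2597 | 0.2592 | 0.2582 | 0.2585 |
| Coverage %, nested ML | 94.7 | 92.8 | 94.2 | 95.3 |
| Coverage %, fixed effects | 95.7 | 94.0 | 95.3 | 95.7 |

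SE ratios, nested ML to fixed: 0.2516/0.2597 = 0.969, then 0.974, 0.979 and 0.983, so about 2–3% smaller. The Monte Carlo SE of a coverage figure is about √(0.95 × 0.05 / 600) = 0.9 points. The empirical SD of the estimate differs by at most 0.0014 between the three analyses in any setting.

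**Step 5: where the SE gap comes from.** The fixed-effects comparison used least squares, with residual divisor 60 − 5 = 55 and a t reference. The ML fit divides by 60 and uses 1.96. With three fixed terms, the ML divisor alone gives √(57/60) = 0.975, a 2.5% reduction. The fixed-effects model fitted by ML would have SEs √(55/60) = 0.957 times those shown, for example 0.2597 × 0.957 = 0.2486. The gap therefore reflects how the residual variance is estimated, not mainly the choice between random and fixed strata.

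**The case against.** The strongest reply is that little depends on this model. Section 6.2 says the outcomes are not collected to draw conclusions about efficacy, and Section 11.1 makes description the main focus. The progression criteria in Section 8 (recruitment, retention, sessions received) do not use it. The strata drop out mainly when they hardly predict outcome, and omitting them then costs almost nothing (SE 0.2599 against 0.2597 at no difference). All of this stands, and it limits the severity.

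Stronger readings are tempting, but the documents do not support them:

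- *The variances cannot be estimated.* They can, with almost no precision.
- *The strata will usually be dropped.* The high rates for at least one zero variance do not show this. In the nested fit, a zero centre variance with a positive mode-within-centre variance still adjusts through the four cells. Both variances are zero in half of trials or more only under ML with differences up to about 0.2 SD, or under nested REML with none.
- *The loss would be silent.* A zero variance shows in the output. The gap is that the SAP does not say what follows.
- *The model will fail to converge.* No check here shows that.
- *The treatment estimate is invalid.* Its spread hardly changes between the analyses.

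The code is also imperfectly legible. Nesting follows from the listed order, but an estimation option could have been lost. That is why REML and the crossed model are shown; both leave the same pattern.

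**Conclusion.** The point holds as a specification weakness of minor to moderate weight; it is not one that must be fixed before the analysis can be trusted. Two stratification factors with two levels each are fitted as random effects, and each variance rests on one degree of freedom (two for mode if nested). Under the assumed differences, adjustment is fully lost in 64% of trials down to 0% under nested ML, and in 50% down to 0% under nested REML. Whether and how far the strata are adjusted for is left to the data, outcome by outcome, and text and code describe different structures.

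The effect on the treatment contrast is small: SEs about 2–3% lower and coverage 92.8–95.3% against 94.0–95.7%. Much of even that comes from ML and the normal reference. The case for change is a determinate model that matches its text, not a material gain in precision. The percentages rest on the assumed stratum differences, the balanced centres and the simplification to participant means.

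**What to change.** Fit centre and delivery mode as fixed effects and keep only the participant random intercept:

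`mixed sims sims_b i.letstalk##i.TimePoint i.CentreNo i.deleverymode || StudyNo:`

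Change Section 11.4 to match: baseline score, time, treatment, treatment by time, centre and mode as fixed effects; participant as the only random effect. This also settles the nested-or-crossed question. State the estimation method in the same sentence. If intervals like those of the fixed-effects comparison are wanted, specify REML with small-sample degrees of freedom, because ML would keep the slightly small SEs (step 5).

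If random effects are retained, the minimum is to say whether mode is nested or crossed, and to state that both factors enter as fixed effects if a variance is estimated as zero.

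Cost: two parameters and one line of text and code. No data collection or design feature changes.
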